**D2.2.3 - Study Protocol for P3-C1-005**

**Author(s):** [name] [name]

**Version:** V2.1

**Dissemination level:** Public

Concept ID	Concept Code	Concept Name	Domain	Vocabulary
256036	31920006	Hemorrhagic varicella pneumonitis	Condition	SNOMED
4026139	197367007	Hepatic granulomas in berylliosis	Condition	SNOMED
4119929	233744008	Hilar lymph node sarcoidosis	Condition	SNOMED
37110889	725415009	House allergic alveolitis	Condition	SNOMED
4121299	233774000	Humidifier fever	Condition	SNOMED
434670	48347002	Humidifier lung	Condition	SNOMED
4243675	59940009	Hypersensitivity alveolitis in lungworm infection	Condition	SNOMED
4176753	428697002	Inactive tuberculosis of lung	Condition	SNOMED
260936	186175002	Infiltrative lung tuberculosis	Condition	SNOMED
3168004	1.773E+16	Inhalation injury due to anhydrous ammonia	Condition	Nebraska Lexicon
3170305	9.55E+15	Inhalation lung injury due to chlorine	Condition	Nebraska Lexicon
765178	1.29211E+14	Isoniazid resistant tuberculosis of lung	Condition	SNOMED
4272230	36696005	Kaolinosis	Condition	SNOMED
4250618	7343008	Liparitosis	Condition	SNOMED
4081069	238676008	Lofgrens syndrome	Condition	SNOMED
4120263	233696002	Lycoperdonosis	Condition	SNOMED
4315046	86649001	Meconium pneumonitis	Condition	SNOMED
4309159	213223003	Mendelson's syndrome as a complication of care	Condition	SNOMED
4188630	47386001	Mendelson's syndrome resulting from a procedure	Condition	SNOMED
4151351	28295001	Middle lobe syndrome	Condition	SNOMED
4052548	233623000	Mononuclear interstitial pneumonia	Condition	SNOMED
45768849	707370001	Multiple hyalinizing granuloma of lung	Condition	SNOMED
4227290	87695000	Necrotizing bronchiolitis	Condition	SNOMED
4120264	233697006	New Guinea lung	Condition	SNOMED
255175	80602006	Nodular tuberculosis of lung	Condition	SNOMED

Concept ID	Concept Code	Concept Name	Domain	Vocabulary
4021760	105977003	Non-infectious pneumonia	Condition	SNOMED
4222731	40100001	Obliterative bronchiolitis	Condition	SNOMED
4112832	195989002	Pituitary snuff-takers' disease	Condition	SNOMED
45768851	707373004	Plasma cell granuloma of lung	Condition	SNOMED
4112676	196017002	Pneumoconiosis associated with tuberculosis	Condition	SNOMED
254561	38976008	Pneumonic plague	Condition	SNOMED
444099	46207001	Pneumonitis due to acquired toxoplasmosis	Condition	SNOMED
42536542	735466008	Pneumonitis due to aspiration of blood	Condition	SNOMED
36712850	1.2571E+13	Pneumonitis due to Herpes zoster	Condition	SNOMED
4311410	86294001	Pneumonitis due to inhalation of essence	Condition	SNOMED
4112683	196034005	Pneumonitis due to inhalation of milk	Condition	SNOMED
4112839	196033004	Pneumonitis due to inhalation of regurgitated food	Condition	SNOMED
4110180	196035006	Pneumonitis due to inhalation of vomitus	Condition	SNOMED
442297	57463004	Pneumonitis due to inhaled liquid	Condition	SNOMED
255735	35339003	Primary pneumonic plague	Condition	SNOMED
42572644	3.36161E+14	Pulmonary abscess due to Rhodococcus	Condition	SNOMED Veterinary
4138244	32204007	Pulmonary actinobacillosis	Condition	SNOMED
258354	187052004	Pulmonary African histoplasmosis	Condition	SNOMED
4077129	17993000	Pulmonary arteritis	Condition	SNOMED
4296039	76846002	Pulmonary endarteritis	Condition	SNOMED
4102140	28122003	Pulmonary eosinophilic granuloma	Condition	SNOMED
4345699	240387006	Pulmonary glanders	Condition	SNOMED
46269691	1.01401E+14	Pulmonary granuloma	Condition	SNOMED
4119928	233742007	Pulmonary hyalinizing granuloma	Condition	SNOMED
44783637	697921005	Pulmonary hypertension in sarcoidosis	Condition	SNOMED

**D2.2.3 - Study Protocol for P3-C1-005**

**Author(s):** [name] [name]

**Version:** V2.1

**Dissemination level:** Public

Concept ID	Concept Code	Concept Name	Domain	Vocabulary
4345215	240391001	Pulmonary melioidosis	Condition	SNOMED
4051334	233614003	Pulmonary mucormycosis	Condition	SNOMED
253954	154283005	Pulmonary tuberculosis	Condition	SNOMED
258061	45556008	Pulmonary tularemia	Condition	SNOMED
4119785	233699009	Pyrethrum alveolitis	Condition	SNOMED
40490351	446946005	Reinfection pulmonary tuberculosis	Condition	SNOMED
40490814	447006007	Relapse pulmonary tuberculosis	Condition	SNOMED
4237921	57089007	Respiratory syncytial virus bronchiolitis	Condition	SNOMED
3175074	2.47E+16	Right lower lobe pneumonitis	Condition	Nebraska Lexicon
4119936	233772001	Sarcoid pulmonary calcification	Condition	SNOMED
4053655	1259003	Schistosomiasis	Condition	SNOMED
442637	67525007	Secondary pneumonic plague	Condition	SNOMED
4077734	19076009	Sick building syndrome	Condition	SNOMED
4119932	233763009	Silicotuberculosis	Condition	SNOMED
45768848	707369002	Single hyalinizing granuloma of lung	Condition	SNOMED
4330286	22482002	Subacute obliterative bronchiolitis	Condition	SNOMED
3654572	836478002	Subacute obliterative bronchiolitis due to chemical fumes	Condition	SNOMED
3654573	836479005	Subacute obliterative bronchiolitis due to vapor	Condition	SNOMED
4112837	196027008	Toxic bronchiolitis obliterans	Condition	SNOMED
4159649	371043007	Toxic inhalation injury	Condition	SNOMED
4089507	187196002	Toxoplasma pneumonitis	Condition	SNOMED
4008132	12181002	Tropical pulmonary alveolitis	Condition	SNOMED
4081994	278484009	Tropical pulmonary eosinophilia	Condition	SNOMED
4251772	74387008	Tuberculosis of hilar lymph nodes	Condition	SNOMED
260315	186177005	Tuberculosis of lung with cavitation	Condition	SNOMED

	D2.2.3 - Study Protocol for P3-C1-005	
	Author(s): [name] [name]	Version: V2.1
	Dissemination level: Public	

Concept ID	Concept Code	Concept Name	Domain	Vocabulary
4304867	81554001	Tuberculosis of lung with involvement of bronchus	Condition	SNOMED
260630	186204008	Tuberculosis of lung, bacteriological and histological examination not done	Condition	SNOMED
4091167	186203002	Tuberculosis of lung, bacteriologically and histologically negative	Condition	SNOMED
253121	186194007	Tuberculosis of lung, confirmed by culture only	Condition	SNOMED
255454	186193001	Tuberculosis of lung, confirmed by sputum microscopy with or without culture	Condition	SNOMED
256018	186195008	Tuberculosis of lung, confirmed histologically	Condition	SNOMED
42600053	4.0621E+13	Bronchointerstitial pneumonia	Condition	SNOMED Veterinary
42599152	3.47351E+14	Hypersensitivity pneumonitis due to inhalation of Micropolyspora faeni spores	Condition	SNOMED Veterinary

	D2.2.3 - Study Protocol for P3-C1-005	
	Author(s): [name] [name]	Version: V2.1
	Dissemination level: Public	

**Table S2 Feasibility person counts for ILD per database**

concept_id	concept_name	BIFAP	CDW Bordeaux	CPRD GOLD	IQVIA - DA Germany
4119786	Interstitial lung disease	7900	3900	6900	8800
253506	Pneumonitis	100	100	2200	100
253797	Post-inflammatory pulmonary fibrosis	10600		1000	
256036	Hemorrhagic varicella pneumonitis	200			
258564	Perinatal interstitial emphysema	100	100		100
260434	Acute radiation pneumonitis	300		300	600
435853	Pulmonary alveolar proteinosis	100		100	
437313	Rheumatic pneumonia	100			
438782	Idiopathic pulmonary hemosiderosis	100		100	
439298	Bronchitis and pneumonitis due to chemical fumes	300	100	100	1200
440748	Interstitial emphysema of lung	800		200	
444084	Extrinsic allergic alveolitis	2300	100	1900	5000
3655088	Pneumonitis caused by inhalation of oil	200		100	
3655110	Pneumonitis caused by fumes	100			
3655111	Pneumonitis caused by vapors	200			
4025168	Diffuse interstitial pulmonary fibrosis	300		7300	
4028118	Diffuse interstitial rheumatoid disease of lung			200	
4044215	Nonspecific interstitial pneumonia	600			
4045227	Respiratory bronchiolitis associated interstitial lung disease	100		200	
4089507	Toxoplasma pneumonitis				100
4110180	Pneumonitis due to inhalation of vomitus			500	
4110182	Acute drug-induced interstitial lung disorder	200	100	100	200
4112678	Acute pneumonitis due to chemical fumes			100	
4112681	Chronic pulmonary fibrosis due to chemical fumes			100	
4112809	Aspiration pneumonitis due to anesthesia during labor and delivery				100
4112813	Drug-induced interstitial lung disorder	100		200	200
4112814	Chronic drug-induced interstitial lung disorders	100		100	100

**D2.2.3 - Study Protocol for P3-C1-005**

**Author(s):** [name] [name]

**Version:** V2.1

**Dissemination level:** Public

concept_id	concept_name	BIFAP	CDW Bordeaux	CPRD GOLD	IQVIA - DA Germany
4112839	Pneumonitis due to inhalation of regurgitated food			100	
4119796	Toxic pneumonitis	200			
4140472	Drug-induced pneumonitis	100			
4148529	Primary atypical interstitial pneumonia	100			
4187218	Pneumonitis due to inhaled substance	49500	12200	500	12400
4195014	Lymphoid interstitial pneumonia	100		100	
4218175	Lipoid pneumonitis			100	
4221865	Radiation pneumonitis	200			
4226132	Post-radiotherapy pneumonitis	100			
4236182	Interstitial pulmonary fibrosis of prematurity			100	
4236725	Pulmonary fibrosis due to and following radiotherapy	100			
4273378	Interstitial pneumonia	200		1300	
4306082	Aspiration pneumonitis	3100		7800	
4311555	Desquamative interstitial pneumonia	100			
4341520	Acute interstitial pneumonia	300			
36714118	Cryptogenic organizing pneumonia	800		500	
37208102	PF-ILD-progressive fibrosing interstitial lung disease				
45763749	Idiopathic interstitial pneumonia	1300			
45763750	Idiopathic pulmonary fibrosis	9100		4300	
45771019	Neuroendocrine cell hyperplasia of infancy	100			
46272927	Interstitial lung disease due to connective tissue disease			100	
46274046	Chemical pneumonitis caused by anesthesia	100	200		100

	D2.2.3 - Study Protocol for P3-C1-005	
	Author(s): [name] [name]	Version: V2.1
	Dissemination level: Public	

**Table S3. Preliminary codes for comorbidities**

Concept name	Concept ID (SNOMED)	Descendants
COPD	255573	yes
Emphysema	261325	yes
Rheumatoid arthritis	80809	yes
Sclerodermia	40352976	yes
Systemic Lupus Erythematosus	257628	yes
Polymyositis/dermatomyositis	80800, 80182	yes
Granulomatosis with polyangiitis	313223	yes
Gastro-oesophageal reflux disease	318800	yes
Hepatitis B/C	40483136	yes
Cancer/malignancy	443392	yes

	D2.2.3 - Study Protocol for P3-C1-005	
	Author(s): [name], [name]	Version: V2.1
	Dissemination level: Public	

**Table S4. Preliminary codes for medications as risk factor for ILD**

Concept name	Concept ID (RxNorm)	Descendants	Excluded
Chemotherapy	TBC		
Amiodarone	1309944	yes	
Immune checkpoint inhibitors (ICIs)	40238188, 741851, 45892628, 45775965, 42629079, 1593273, 1594034, 35200783, 1536789	yes	
Tyrosine kinase inhibitors (TKIs including EGFR inhibitors)	40242675, 1325363, 1319193, 43533090, 35605522, 36853448, 43009062, 35884401, 36851588, 701915, 36861628	yes	
Mammalian target rapamycin (mTOR) inhibitors	9011440, 19092845, 36851551, 19034726	yes	
Rituximab	1309944	yes	
Statins	1545958, 1539403, 1592085, 1551860, 1549686, 1592180, 1510813, 40165636	yes	
Methotrexate	1305058	yes	
Nitrofurantoin	920293	yes	
Tumor necrosis factor (TNF)- $\alpha$ antagonists	1119119, 912263, 1151789, 937368, 19041065, 36855655, 36853282	yes	

TBC= to be confirmed

	D2.2.3 - Study Protocol for P3-C1-005	
	Author(s): [name], [name]	Version: V2.1
	Dissemination level: Public	

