#### Covariates for the patient-level characterisation study

As part of patient-level characterisation study, comorbidities will be measured in the period of 365 days prior to the index date (i.e. date of diagnosis of ILD). Concomitant medications will be measured within 30 and 365 days prior to the index date and reported for both time periods.

Covariates used to describe Patient characterisation consist of the following:

- Sex
- Age at index date (i.e. date of diagnosis of ILD). Age will be presented in age categories namely:
  - <18
  - 18-39
  - 40-59
  - 60-79
  - >=80 years.
- ILD subtypes:
  - alveolitis/pneumonitis (excluding aspiration and infectious pneumonitis)
  - lung fibrosis
  - drug-induced

	D2.2.3 - Study Protocol for P3-C1-005	
	Author(s): [name] [name]	Version: V2.1
	Dissemination level: Public	

- Unspecified ILD
- description of the top 10 of the most frequent comorbidities and concomitant medications using large-scale characterisation, as specified in the CohortCharacteristics R package and assessed in the period of 365 days prior to the index date.
- Comorbidities of interest (Gaillet, Favelle et al. 2015, Choi, Dauti et al. 2018, Joy, Arbiv et al. 2023), in particular:
  - COPD/emphysema
  - Connective tissue disease namely rheumatoid arthritis, sclerodermia, systemic lupus erythematosus (SLE), polymyositis/dermatomyositis, granulomatosis with polyangiitis (GPA)
  - GERD
  - Hepatitis B/C
  - Cancer excluding non-melanoma skin cancer
- Use of concomitant medication (assessed in the 30 days and 365 days prior to the index date) in particular:
  - chemotherapy
  - amiodarone
  - immune checkpoint inhibitors (ICIs)
  - tyrosine kinase inhibitors (TKIs including crizotinib, EGFR inhibitors, erlotinib, gefitinib)
  - mammalian target rapamycin (mTOR) inhibitors
  - rituximab
  - statins
  - methotrexate
  - nitrofurantoin
  - tumor necrosis factor (TNF)- $\alpha$  antagonists (Paolo, Philippe et al. 2022).

The operational definition of the covariates is described in [Table 7](#). Index date is the start of the incident ILD diagnosis during the study period. The preliminary concepts for prespecified conditions and drugs of interest are described in [Appendix I](#).

	D2.2.3 - Study Protocol for P3-C1-005	
	Author(s): [name] [name]	Version: V2.1
	Dissemination level: Public	

**Table 7.** Operational Definitions of Covariates.

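### Table S4 prints a probably truncated mTOR inhibitor ID (9011440) and gives Amiodarone and Rituximab the same ID, so the Table S3 and S4 IDs need a vocabulary check before the code is run

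*Protocol*

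**What the plan says.** Section 8.6.3 names the drugs to be described in patients with newly diagnosed ILD, among them "mammalian target rapamycin (mTOR) inhibitors", amiodarone and rituximab. Table 7 sets two windows for them, 30 and 365 days up to the index date. On the code lists, Section 8.6.3 says: "The preliminary concepts for prespecified conditions and drugs of interest are described in" Appendix I.

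In Appendix I, Table S4 gives the mTOR row four IDs with descendants: "9011440, 19092845, 36851551, 19034726". The Amiodarone row and the Rituximab row each hold one ID, and it is the same one, 1309944. Chemotherapy is the only row marked as still to be confirmed.

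Table S3 does the same for comorbidities. The rows relevant here are "Hepatitis B/C 40483136 yes", "Polymyositis/dermatomyositis 80800, 80182 yes" and "Cancer/malignancy 443392 yes".

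Both tables carry the word preliminary in their titles: "Table S3. Preliminary codes for comorbidities" and "Table S4. Preliminary codes for medications as risk factor for ILD". Neither gives a name for each ID.

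**The concern.** A concept ID with a missing digit need not stop a query. It can return no records, or the records of some other concept, and the table of results looks normal either way. The drugs in Table S4 are the prespecified medication risk factors of objective 2. According to Section 6, the study is meant to support signal validation for drug-induced ILD, so the recorded use of these drugs is one of the results that will be read closely.

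An error here would be hard to see in the output. Section 11 already expects drugs given mainly in hospital to be poorly captured in primary care, and counts below 5 are masked under Section 8.8.2. A low mTOR inhibitor count could be put down to either. The study code is common to all data partners, so a wrong ID would be used at every site, although its effect would differ with local use of the drug.

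**Working it through.** The protocol states no figure to reproduce. The check is a tabulation of the IDs as printed.

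**1. Entries in Table S4, by row.** Amiodarone 1, immune checkpoint inhibitors 9, tyrosine kinase inhibitors 11, mTOR inhibitors 4, rituximab 1, statins 8, methotrexate 1, nitrofurantoin 1, TNF-α antagonists 7. Total: 1 + 9 + 11 + 4 + 1 + 8 + 1 + 1 + 7 = 43. Chemotherapy has none.

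**2. By length.**

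| Digits | Entries |
|---|---|
| 8 | 20 |
| 7 | 18 |
| 6 | 5 |

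Seven digits is therefore an ordinary length, and length alone shows nothing.

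**3. By leading digit.** Of the 18 seven-digit entries, 17 start with 1 (1309944 counted twice). The exception is 9011440. The other IDs starting with 9 are 920293, 912263 and 937368, all of six digits.

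**4. Neighbours.** Three IDs in the table start with 190, all of eight digits: 19092845 and 19034726 in the mTOR row itself, and 19041065 in the TNF row. A leading 1 put before 9011440 gives 19011440, which falls in that block. A lost first digit is the simplest explanation. The documents cannot confirm it.

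**5. Duplicates.** One ID occurs in two rows of Table S4: 1309944, for Amiodarone and for Rituximab. One concept with its descendants cannot be the correct definition of two different drugs. Run as printed, the two rows would return identical counts in each database. Each row has only this ID, so a wrong row would report another concept entirely.

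**6. Other slips in the same appendix.** Table S1.A prints 4223637 for both carbon electrode makers' pneumoconiosis and cerium pneumoconiosis, with different concept codes (40218008 and 233754007). ID errors therefore did reach this version.

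**7. Size for the mTOR row.** If 9011440 matches nothing,

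share missed = (users found only through the intended first ID) / (users of any of the four intended drugs).

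The protocol gives neither number. The share is 0% where that drug is not recorded and 100% where it is the only one recorded. If the printed ID resolves to another drug, the count could rise instead.

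**8. Hepatitis B/C.** In Table S3, 9 of 10 rows hold one ID with descendants, and only Polymyositis/dermatomyositis holds two. The protocol does not say what 40483136 covers.

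**The case against.** The strongest reply is that the lists are labelled preliminary and that Section 8.8.1 requires test runs and quality control checks before the package is released. Looking up IDs is normal work at that stage. This limits the point to verification and correction, but does not remove it. V2.1 is described in the document history as the final version. It is dated 11/07/2024, while the milestones place both code creation and execution in June 2024. The protocol names no later step that finalises the lists. None of the checks it describes is a comparison of each ID with its drug name, and the drug-exposure diagnostics tool mentioned in Section 8.2 is not among the packages named in Section 10.

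It is also fair to say that the truncation is inferred from a digit pattern, and that a digit can be lost when a PDF table is read as text. The page itself should be looked at first. This stands, and is why the mTOR ID is called probable rather than shown. It does not touch the duplicated 1309944.

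A reader might go further and infer that the Hepatitis B/C row is also wrong, since Polymyositis/dermatomyositis has one ID per disease and COPD and emphysema have separate rows. The documents do not support that. One ID with descendants is the usual form in Table S3, a single parent concept may cover both infections, and no rule requires one ID per disease. Nor do they support saying that the mTOR figure will certainly be wrong, that any error must lower it, or that it would be equally wrong in every database.

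**Conclusion.** The point holds in a limited form. One error is certain from the document: at least one of the Amiodarone and Rituximab rows carries the wrong ID. One is probable: 9011440 has lost a leading digit. The second rests on the pattern in the table and on the printed page agreeing with the text, and only the vocabulary can settle it. If it is wrong, one of four mTOR IDs is affected, by an amount the documents do not give and which may be zero in some databases. The Hepatitis B/C ID is a query to confirm, not a finding.

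The consequences are confined to the medication description under objective 2. Incidence and survival do not use Tables S3 or S4.

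**What to change.** Before the study code is released:

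- Look up every ID in Tables S3 and S4 in the vocabulary, and add the concept name beside each so that a reader can see the match.
- Correct 9011440 if it does not resolve to an mTOR inhibitor, and replace 1309944 in whichever of the Amiodarone and Rituximab rows it does not belong to.
- Confirm that 40483136 with descendants covers both hepatitis B and hepatitis C, and amend the row only if it does not.
- State in Section 10 that the code is not run with any ID that fails to resolve to its named drug or disease.

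The milestones place execution before the date of this version. If the code has already been run, compare the IDs actually used with the corrected tables, and repeat the affected rows if they differ.

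The cost is a short vocabulary look-up, edits to a few appendix rows and one sentence in Section 10. No extra data are needed.

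### Table S4 gives amiodarone and rituximab the same concept ID, so at least one of the two rows would not measure its drug if run as printed; Table S3 also lacks the skin cancer exclusion stated in section 8.6.3

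*Protocol*

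**What the plan says.** Section 8.6.3 (covariates for the patient-level characterisation study) lists ten medication groups to be reported for the 30 and 365 days before ILD diagnosis. Amiodarone and rituximab are separate entries. The same section lists the comorbidities of interest, among them "Cancer excluding non-melanoma skin cancer". For the codes it points to Appendix I: "The preliminary concepts for prespecified conditions and drugs of interest are described in" that appendix.

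In Appendix I, Table S4 has the columns "Concept name Concept ID (RxNorm) Descendants Excluded". Two of its rows read "Amiodarone 1309944 yes" and "Rituximab 1309944 yes", both with nothing under exclusions. Chemotherapy is the only row marked as to be confirmed.

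Table S3 has the columns "Concept name Concept ID (SNOMED) Descendants" and no column for exclusions. Its cancer row reads "Cancer/malignancy 443392 yes".

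Section 8.8.5 says that N and % will be given for each drug and condition of interest, by database, overall and by age group and sex where counts allow. Objective 2 is repeated for three ILD subtypes (Table 1), and section 8.8.3 says it can be explored in all participating databases.

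**The concern.** One ingredient ID cannot stand for two different drugs. If the analysis package takes Table S4 as it is printed, one of the two drugs has no valid prespecified estimate, and the row that carries its name reports the other drug, or possibly neither row is right. The error would be easy to miss. Section 11 already expects some ILD-related medicines given mainly in hospital to be poorly captured in primary care data, and counts below 5 are masked, so an odd count need not raise suspicion.

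This touches the study's purpose. The rationale in section 6 says that describing medications around diagnosis should help in validating signals of drug-induced ILD, and it names antiarrhythmics and biologics among the drug classes concerned. Table S4 itself presents its drugs as risk factors for ILD. A mislabelled row in the baseline table would misinform that use.

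The cancer row raises a smaller question of the same kind: the text and the code list define the covariate differently.

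**Working it through.** No sample size, power or error rate is involved, and the plan states no figure to reproduce. The check is a count of IDs and a comparison of text with table.

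**1. Duplicate IDs in Table S4.** ID entries by row:

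| Drug group | IDs listed |
|---|---|
| Chemotherapy | none (to be confirmed) |
| Amiodarone | 1 |
| Immune checkpoint inhibitors | 9 |
| Tyrosine kinase inhibitors | 11 |
| mTOR inhibitors | 4 |
| Rituximab | 1 |
| Statins | 8 |
| Methotrexate | 1 |
| Nitrofurantoin | 1 |
| TNF-α antagonists | 7 |

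Entries: 1 + 9 + 11 + 4 + 1 + 8 + 1 + 1 + 7 = 43. Distinct IDs: 42. The one duplicate is 1309944, shared by amiodarone and rituximab. Since it is each row's only ID, and both rows take descendants and exclude nothing, the two definitions are the same set of codes.

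**2. Reach of the duplicate.** Identical definitions give identical results wherever the two rows are reported. Objective 2 covers 4 databases, 2 windows (30 and 365 days) and 4 patient groups (ILD overall plus the three subtypes in Table 1). That is 4 × 2 × 4 = 32 pairs of equal figures before stratification by age and sex, which adds more. Where a count is masked, it is masked in both rows.

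**3. Which row is wrong.** The vocabulary is not in the protocol, so the documents do not show which drug, if either, 1309944 identifies. They support only the statement that at least one row is wrong.

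**4. Cancer.** Table S3 holds 11 IDs in ten rows, with no duplicate and no exclusion. Side by side:

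| Place | Definition |
|---|---|
| Section 8.6.3 | cancer without non-melanoma skin cancer |
| Table S3 | 443392 and all descendants, nothing removed |

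No other part of the protocol supplies the exclusion. If non-melanoma skin cancer concepts descend from 443392, the printed definition contains the one in the text. Cancer prevalence under Table S3 would then be equal to or above that under section 8.6.3, by the share of patients whose only malignancy record in the window is a non-melanoma skin cancer. The protocol gives no count from which to compute that share. If those concepts do not descend from 443392, there is no numerical effect.

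**5. Other objectives.** Incidence and survival are stratified by age, sex and calendar time, not by these covariates, so Objectives 1 and 3 do not use either table.

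**The case against.** The strongest reply is that these lists are not the executed code. Both tables are headed as preliminary, chemotherapy still has no code, and writing the analytical code is a separate milestone in section 5. Section 8.8.1 provides for test runs and quality control before release, section 8.2 describes an ingredient-level drug exposure diagnostic, and section 10 promises peer review and user testing. This stands in part. A reader might infer that the reported prevalences will be wrong; the documents support only that they would be wrong if the lists were run as printed. None of the steps listed undertakes to check that an ID matches its label. The duplicate also remains, without a to-be-confirmed mark, in V2.1 of 11 July 2024, which the document history calls final and which postdates the June 2024 slot for running the code.

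A reader might also infer that one of the drugs is never measured. That goes too far. Large-scale characterisation captures medications independently of Table S4. It is only a partial safeguard, because section 8.6.3 describes just the ten most frequent.

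On cancer, the text definition is explicit, and the missing exclusion may merely reflect a table with no column for it. Calling the cancer prevalence inflated would treat as established that the skin cancer concepts sit under 443392, which is inferred from the label "Cancer/malignancy" and the inclusion of descendants. The mismatch between text and table remains.

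Finally, these are descriptive rows in a study with no hypothesis. That is true and limits the reach. It does not make a mislabelled row acceptable.

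**Conclusion.** The duplicate is a definite error in a code list on which Objective 2 relies: two of ten prespecified drug groups share one definition, and at least one of them does not measure the named drug if the list is run as printed. The size of the error in the prevalence cannot be computed, because the protocol gives no counts for these drugs.

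The cancer mismatch is a secondary point. Its direction, if it has any effect, is upward relative to the text. It rests on the assumption that non-melanoma skin cancer concepts descend from 443392, and its size is not given.

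It would be wrong to read this as a fault in the prespecified risk factors as a whole. The affected rows are two drugs, of which one may be correct, and one comorbidity. Incidence and survival results are untouched.

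**What to change.** - Check 1309944 against the vocabulary, and give amiodarone and rituximab each their own ID in Table S4.
- Add an automated check to the study code that no concept ID serves two drug groups. On the printed list it would flag exactly one ID.
- Add the non-melanoma skin cancer concepts, with descendants, as exclusions under 443392 in Table S3, or amend section 8.6.3 so that text and table agree.
- Establish whether the code has already been executed with these lists. If so, rerun the affected rows in each database.

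Before execution the cost is a vocabulary look-up and two edits to code lists. After execution it also includes a rerun at each data partner, limited to the affected drug rows and the cancer row. Incidence and survival need no rerun.
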